In Person Feedback in Student Health and Counseling Centers. With well documented barriers related to implementing approaches developed in a lab setting or in the context of a research trial to “real world” clinical settings, Study 3 will test the efficacy of the PFI in a Student Counseling and Health Center at a large, diverse public university in the Northeastern U.S. Students presenting with medical and/or mental health concerns will be screened for PSM misuse as well as AOD use as part of their routine care and will be offered either an in-person session, the web-based PFI, or assessment only control based on random assignment. For practical purposes related to staff time in a busy clinical setting, web-based PFI, if effective with this population, would be preferable; however, if in-person PFI outperforms the web-based (or only under certain conditions for certain students), this will help identify how to best serve students who may be struggling. An important aspect of our in-person approach will be to use the student’s past experiences with PSM as a starting point. An MI-trained interventionist will help the student to develop discrepancies, elicit change talk, provide students with opportunities to more thoroughly explore and question their beliefs, and offer alternatives by reviewing their personalized responses. MI has been an effective approach for other interventions, and it is an appropriate modality for this target population. Thus, **Study 3** aims to determine whether and for whom in-person implementation of the PFI is more efficacious than web-based PFI in reducing PSM misuse and co-occurring alcohol and marijuana use. We hypothesize both web- and in-person PFI will be more efficacious than control. We also hypothesize in-person intervention will be more efficacious than web, particularly at long-term follow-up (18-months), given some literature suggesting advantages of in-person PFI emerge over longer periods²⁰⁰. As with Study 2, we expect reductions in perceived benefits and norms of PSM and increases in alternative behaviors will mediate efficacy of both interventions, as will reductions in alcohol and marijuana use. We will explore demographics and PSM motives as moderators of overall and differential efficacy.

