Aim 1: To examine whether perceived norms of PSM differs from the “actual” prevalence as estimated by the screening sample, the actual prevalence will be subtracted from the perceived prevalence. A one-sample t-test will be used to assess whether the difference score is statistically significantly greater than 0. If the difference score is a non-normal distribution, we will instead use a non-parametric Wilcoxon sign rank test.

Aim 2: Evaluate efficacy of interventions. We will first examine effects of the intervention on perceived norms, benefits of PSM, and use of alternative strategies as separate outcomes using linear mixed models (a.k.a. hierarchical linear or multilevel models¹²⁰). This project will have 5 repeated measures, yielding up to 6,000 Level 1 observations (repeated-measures) across 1,200 Level 2 (people). The following equation represents a basic analytic model for Aims 2 and 3:

$$\text{Level 1: } Y_{ti} = \pi_{0i} + \pi_{1i}(\text{Post})_i + \pi_{2i}(\text{Month6})_i + \pi_{3i}(\text{Month12})_i + \pi_{4i}(\text{Month18})_i$$

$$\text{Level 2: } \pi_{0i} = \beta_{00} + \beta_{01}(\text{Tx})_i + \beta_{02}(\text{Site})_i + r_{00i}$$

$$\pi_{1i} = \beta_{10} + \beta_{11}(\text{Tx})_i + \beta_{12}(\text{Site})_i$$

$$\pi_{2i} = \beta_{20} + \beta_{21}(\text{Tx})_i + \beta_{22}(\text{Site})_i$$

$$\pi_{3i} = \beta_{30} + \beta_{31}(\text{Tx})_i + \beta_{32}(\text{Site})_i$$

$$\pi_{4i} = \beta_{40} + \beta_{41}(\text{Tx})_i + \beta_{42}(\text{Site})_i$$

where *Post*, *Month6*, *Month12*, and *Month18* are dummy codes for follow-up visit such that the reference time point is baseline; *Tx* represents randomly assigned treatment condition; *Site* represents the study site; *i* indexes participants; *r_{00i}* represents a random effect for the intercept; and *Y_{ti}* represents the outcome for each individual, *i*, at each time, *t*. $\beta_{11} - \beta_{41}$ are primary coefficients as they compare treatment conditions for the difference in the outcomes from baseline to each of the follow-up visits. The model assumes conditional independence, given random-effects and (multivariate) normality of Level 2 random-effects. As additional analyses, we will also specify time as a continuous variable in order to assess differences between intervention and control groups in slopes over time.

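### The linear mixed models have only a random intercept, and the slope analysis names no random slope; if correlation between visits decays, the 18-month and slope standard errors are too small and the 6-month ones too large.

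*Combined protocol and SAP*

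**What the plan says.** In the Data Analysis section, Aim 2 begins with the linear outcomes: "We will first examine effects of the intervention on perceived norms, benefits of PSM, and use of alternative strategies as separate outcomes". The model is introduced this way: "The following equation represents a basic analytic model for Aims 2 and 3". Its Level 2 equations hold a single random term, r_00i, which "represents a random effect for the intercept". The four equations for the visit effects contain treatment and site only. The residual assumption follows: "The model assumes conditional independence, given random-effects and (multivariate) normality of Level 2 random-effects".

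The treatment-by-visit terms β11 to β41 "are primary coefficients as they compare treatment conditions for the difference in the outcomes from baseline to each of the follow-up visits". As an additional analysis, "we will also specify time as a continuous variable in order to assess differences between intervention and control groups in slopes". The random effects of that second model are not stated.

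The documents name no unstructured or serial covariance, random slope or robust standard error. They give no between-visit correlation or variance component. The Study Methodology Overview lists perceived norms and benefits among the outcomes to be evaluated at 6, 12 and 18 months.

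**The concern.** A random intercept with conditionally independent residuals is compound symmetry. Baseline is taken to correlate with month 18 exactly as strongly as with month 6. In repeated behavioural and attitudinal measures over 18 months, correlation usually falls as the gap widens, and people usually differ in their trends.

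Each primary coefficient is a difference in change from baseline, so its true variance depends on the correlation at that particular lag. A compound-symmetry fit gives every such contrast the same average variance. If correlation decays, that average is too large for the 6-month contrast and too small for the 18-month contrast. A slope model without a random slope has the same fault in stronger form. At stake are the false-positive rate for long-term effects on norms and benefits, and some power at 6 months.

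**Working it through.** **Plan's own figures.** 5 measures × 1,200 people = 6,000 observations, as stated. The only power figure for Aim 2 (above 0.80 with 600 per arm) is for the Poisson model, and its baseline mean and variance components are not reported. It cannot be used to check the linear models.

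**Inputs.** Visits at 0, 6, 12 and 18 months (Study 2 Baseline and Randomization). Two-sided level .05 (the Power section gives p < .05; two-sided is assumed). Equal variances, complete data and all correlations are assumptions.

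**Change from baseline.** With r6, r12 and r18 the correlations at each lag, the mean correlation over the six pairs is r̄ = (3·r6 + 2·r12 + r18)/6. A random-intercept fit estimates the residual variance as σ²(1 − r̄).

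- Model variance of a change: 2σ²(1 − r̄). True variance at lag k: 2σ²(1 − r_k). The factor for arm size cancels.
- SE ratio (model/true) = √[(1 − r̄)/(1 − r_k)]. Actual level = 2[1 − Φ(1.96 × ratio)].

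For .6/.5/.4: r̄ = (1.8 + 1.0 + 0.4)/6 = .533.

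- Month 6: √(.467/.4) = 1.080, level .034.
- Month 12: √(.467/.5) = .966, level .058.
- Month 18: √(.467/.6) = .882, level .084.

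**Slope without a random slope.** Centred times c are −9, −3, 3, 9, with sum of squares 180. The true slope variance is proportional to c′Rc = 180 + 90·r6 − 108·r12 − 162·r18; the model uses 180(1 − r̄).

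For .6/.5/.4: c′Rc = 180 + 54 − 54 − 64.8 = 115.2, and the model value is 180 × .4667 = 84. The ratio is √(84/115.2) = .854, level .094.

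**Range of assumptions: SE ratio (actual level)**

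| Correlations | Month 6 | Month 12 | Month 18 | Slope |
|---|---|---|---|---|
| Equal | 1.00 (.050) | 1.00 (.050) | 1.00 (.050) | 1.00 (.050) |
| .6/.55/.5 | 1.041 (.041) | .981 (.054) | .931 (.068) | .913 (.074) |
| .6/.5/.4 | 1.080 (.034) | .966 (.058) | .882 (.084) | .854 (.094) |
| AR(1), .6 per 6 months | 1.166 (.022) | .922 (.071) | .833 (.103) | .782 (.125) |
| Baseline .4 with each follow-up, follow-ups .6 with each other | .913 (.074) | .913 (.074) | .913 (.074) | .928 (.069) |
| 12-month lag .65, others .55 | .962 (.059) | 1.091 (.032) | .962 (.059) | 1.034 (.043) |

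**Checks.** Sixty simulated datasets with AR(1) correlation .7, 1,200 people and 10% random missingness, fitted with a random-intercept model, gave ratios of 1.14, 0.95, 0.74 and 0.70 for months 6, 12, 18 and slope. The formulas give 1.20, 0.92, 0.81 and 0.76; Monte Carlo error is about 9%. The equation also contains a *Post* visit. Placing it at an assumed 1 or 3 months leaves the directions under decay unchanged but makes the slope worse: with linear decay .7/.6/.5 the slope ratio falls from 0.82 with four visits to 0.75–0.76 with five.

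**The case against.** The strongest reply is that the documents give no correlations, so no error is demonstrated. That stands as a limit. A reader might infer that the model necessarily makes the 18-month and slope standard errors too small and the 6-month ones too large. The text does not support this: equal correlation gives no error, and in the last two rows of the table the month 6 standard error is too small. In the last row the slope standard error is slightly too large.

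Second, a reader might infer that the slope analysis is planned with a random intercept only. Its random effects are simply not given. The written equation is the visit-dummy version and is presented as a basic model, and the reference to multivariate normality of random effects does not exclude further ones. The slope figures therefore apply only if no random slope is added. For the visit model the reply is weaker: the equation is the only specification given, and it is reused for Aim 3.

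Third, it is tempting to tie this to the Study 3 hypothesis that in-person feedback is better at 18 months (In Person Feedback in Student Health and Counseling Centers). That hypothesis concerns stimulant misuse and co-occurring alcohol and marijuana use, which are analysed with Poisson models. No level was calculated for those models, so neither harm to that comparison nor a change to the count models follows from this check.

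Finally, the measures table labels norms and attitudes as mediators, and the slope model is an additional analysis. Both reduce the weight of the point. The Study Methodology Overview nonetheless lists norms and benefits as outcomes at all three follow-ups.

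**Conclusion.** The point holds in conditional form. As written, the linear mixed models impose one correlation across all visits, with no safeguard, and the slope analysis leaves its random effects unstated. If correlation decays as in the two moderate patterns (.6/.55/.5 and .6/.5/.4), the actual level at nominal .05 is .068 to .084 at month 18 and .074 to .094 for a slope without a random slope. Month 12 stays near nominal (.054 to .058) and month 6 is conservative (.041 to .034). These figures rest on assumed correlations, four equally spaced visits, equal variances and complete data. The consequence is modest and confined to the norms, benefits and strategies outcomes and their slope analysis. Because correction is cheap, it should be made.

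**What to change.** For the linear mixed models, specify an unstructured covariance across visits. It needs 10 parameters for four visits (4 × 5/2), or 15 if the *Post* visit is kept (5 × 6/2), few against 1,200 participants. For Study 3, with 300 participants, name a fallback in advance: a simpler structure with participant-clustered robust standard errors if the unstructured fit does not converge. For the continuous-time analysis, state a random slope, or participant-clustered robust standard errors.

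The change is a few sentences in the analysis plan. The cost is some extra covariance parameters and possible non-convergence in Study 3, which the fallback covers. If the correlations turn out equal, little is lost.

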PSM Misuse and Co-occurrence of AOD. We have consistently shown that PSM misuse is also a marker for heavy AOD involvement as it seldom occurs in isolation^{1, 145-147}. Students who engage in PSM misuse are at risk for a host of issues related to alcohol and marijuana use compared to those who do not use PSM and those who use but do not misuse (i.e., take the PSM as prescribed), including being more likely to have used other drugs, to report frequent binge drinking, and more likely to drive after binge drinking than other college students^{4, 29-30, 33, 36-37, 131}. Adolescents and young adults have particularly high rates of concurrent poly-drug use with up to 90% of past-year PSM misusers reporting using other drugs, particularly marijuana^{31, 33-35}. Students who misuse PSM are more likely to meet diagnostic criteria for dependence on alcohol and marijuana, and are more likely than students abusing other drugs to report any drug related problems and to experience nine out of ten drug related consequences as assessed by the Drug Abuse Screening Test-10 (DAST-10)³²⁻³³. Thus, in addition to harm related to PSM misuse per se, considerable harm is related to the co-occurrence of PSM misuse with excessive alcohol, marijuana, and other drug use.

Dearth of Interventions and Missed Opportunities. Given the prevalence and consequences of PSM misuse on college campuses, the high co-occurrence with alcohol and marijuana, and the academic and public health implications, innovative prevention and treatment approaches are critically necessary^{14, 20, 33, 39-41}. However, there are currently *no documented efficacious interventions* targeting college students who misuse PSM. The proposed study explicitly leverages expert knowledge ([name]) from existing NIDA-funded research on risk factors for PSM with expertise in screening and brief intervention (SBI) for college student alcohol and marijuana misuse by leaders in the field ([name], [name], [name], [name], [name]) to develop and test such an intervention on three college campuses, in order to attack the problem of PSM misuse and bridge this important research and service gap. Consistent with other interventions in the college setting, we propose to

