Participants will complete a battery of web-based follow-up assessments at 6, 12, and 18 months post-baseline for which they will receive \$20, \$25, and \$30, respectively. Participants will additionally complete a brief post-intervention assessment of satisfaction with services and convenience of the intervention, and at each assessment they will be asked whether they have sought other drug treatment since the intervention to control for possible confounding treatment effects. These data will help determine the ideal interventions for the service delivery settings in regard to ease of access and utilization by participants.

Study 3 Training and Ongoing Supervision of Interventionist: One potential method for maintaining or enhancing the efficacy of individual brief interventions for college students seeking campus health and mental health care beyond the life of a research project is to train and supervise existing service providers to deliver the feedback interviews. The current approach will provide training to enhance existing knowledge of the UAlbany Counseling and Health Center staff regarding PSM misuse, and will utilize an existing provider imbedded in the Counseling Center staff at UAlbany to provide the in-person interventions. The provider will complete specific additional training related to both the MI process and PSM, alcohol, and marijuana content of the proposed intervention, and will participate in weekly supervision meetings with Drs. [name] and [name]. In addition, all intervention sessions will be audio-recorded and reviewed for adherence to the protocol and MI competence using existing protocols developed for use in prior funded projects at UAlbany and UW. The interventionist will also complete an adherence checklist after each individual session, to indicate which components were covered in each intervention session. Scores on adherence/competence measures and checklists will be reviewed and included as a covariate in secondary analyses of intervention efficacy.

Measurement and Assessment Procedures: Measures will be completed via a secure web survey, using DatStat Illume and will last 30-45 minutes. Measures selected are in Appendix A.

PSM Measures		
PSM Use	DV	
 PSM Timeline Followback (TLFB) - Quantity and past-30-day frequency of PSM misuse¹⁸⁸ Medical Use, Medical Misuse, and Non-Medical Use Questionnaire^{23, 80}

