PSM Consequences	DV	
 Drug Abuse Screening Test (DAST)³² The CAGE Questionnaire – Stimulant Use¹⁸⁹ Prescription Stimulant Use Consequences⁴
PSM Motivations	Moderator	
 Prescription Stimulant Use Motives Questionnaire⁹¹ Motives for Not Using⁹
PSM Norms and Attitudes	Mediator	
 Prescription Stimulant Norms Rating Form⁷⁴ Attitudes about PSM and Diversion⁴ Prescription Stimulants Expectancy Questionnaire (PSEQ-II)¹⁸⁷
AOD Measures		
AOD Use	DV/Mediator	
 Quantity/Frequency/Peak Alcohol Use Index^b Daily Drinking Questionnaire¹¹³ Alcohol and Marijuana Timeline Followback (TLFB)^{9,10} - Quantity and past-30-day frequency of marijuana and alcohol use, (use days, heavy episodic drinking, and typical and peak BAC ASSIST¹³² - Other drug use
AOD Consequences	DV	
 Rutgers Alcohol Problem Index (RAPI)¹⁹¹ Rutger's Marijuana Problem Index (RMPI)^{169,192,193}
Reasons for Not Using	Moderator	
 Attributions for Limiting or Abstaining from Illicit Drugs (ALAID)⁹
Other Measures		
Demographic Characteristics	Covariate/ Moderators	
 Standard questions will be used to assess age, sex, sexual orientation, race/ethnicity, parental education level, number of hours per week working for pay, religiosity, and current living arrangement
Academic Characteristics, Skills and Outcomes	Feedback	
 Learning and Study Strategies Inventory, 2nd edition (LASSI)¹⁷⁵ Relapse Prevention/Protective Behaviors Scale¹⁹⁰ Satisfaction with Academic Progress and Skills Factors affecting Academic Performance Activities/Options that Could Improve Grades or Academic Progress

		
 ▪ Primary Academic Outcomes: GPA ▪ Academic Behaviors ▪ College Engagement¹⁹⁴
Satisfaction	Covariate	▪ Participants' satisfaction with interventions (assessed post intervention)

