We will then examine effects on PSM, marijuana, and alcohol use and consequences. These outcomes are integers, bounded at zero, and often times positively skewed. Because of potential violations of regression assumptions that can arise due to the non-normal distribution, we will use a generalized form of the linear mixed model (GLMM) with a Poisson distribution in order to more appropriately model these outcomes as counts¹¹⁷. Count regression coefficients are connected to the outcome via a natural log link and are commonly exponentiated (e^β) to yield rate ratios (RRs) describing the proportional increase in the outcome for a 1-unit increase in the predictor (e.g., Treatment (1) compared to Control (0)).

To assess mediation hypotheses, we will utilize an approach that has been used by co-investigators with similar data to the proposed study¹⁹⁷. Kenny et al.¹⁹⁸ described mediation using multilevel models for longitudinal treatment data similar to the present data. Specifically, Kenny et al. focused on change in the direct treatment pathways from a model without the mediator to a model with the mediator (i.e., the common c and c' pathways in the mediation literature). In the present context, that is the treatment cross-level interactions with time ($\beta_{11} - \beta_{41}$) for the model presented above compared to one in which mediators are included as Level 1 time-varying covariates. We will use this approach and consider the percent reduction in effects after the mediator is included in the model. In Neighbors et al¹⁹⁹, this approach was extended using a nonparametric bootstrap¹⁹⁹ to allow estimation of the indirect path without making normality assumptions on the sampling distribution of the indirect effect. Perceived benefits and norms of PSM, use of alternative strategies, and alcohol and marijuana use will be included as the Level 1 time-varying mediators of interest and PSM use and consequences will be modeled as the outcomes. To assess moderators of efficacy, we will include level 2 covariates for baseline levels of motivations of PSM and demographic characteristics as well as their interactions with treatment in the GLMM.

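### The Poisson model for use and consequence outcomes ties the variance to the mean, although 30-day frequencies and the DAST have ceilings, so standard errors will generally be wrong, in a direction the documents cannot settle

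*Combined protocol and SAP*

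**What the plan says.** Data Analysis, Aim 2, describes the PSM, marijuana and alcohol use and consequence outcomes in one sentence: "These outcomes are integers, bounded at zero, and often times positively skewed". It then assigns them all to a "generalized form of the linear mixed model (GLMM) with a Poisson distribution" and a log link. The model equation has a single person-level term, which "represents a random effect for the intercept". The text adds: "The model assumes conditional independence, given random-effects". Aim 3 uses the same Poisson approach for Study 3.

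The measures table (Measurement and Assessment Procedures) defines the frequencies over a fixed window: "Quantity and past-30-day frequency of PSM misuse" for PSM, and "Quantity and past-30-day frequency of marijuana and alcohol use" for the other two substances. It lists the DAST as a consequences outcome without giving its length. The Significance section refers to "nine out of ten drug related consequences as assessed by the Drug Abuse Screening Test-10 (DAST-10") under the same citation number as the measures table, so a ten-item score is a fair inference but is not stated.

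No upper limit, binomial family, dispersion parameter, visit-level random effect or robust standard error is mentioned. The opening of Data Analysis plans descriptive checks of distributions but attaches no decision to them.

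**The concern.** A Poisson random-intercept model allows no free variance around a student's own level: at each visit the variance must equal the mean. Two features of these outcomes break that in opposite directions.

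- A ceiling reduces variance. A student who reports about 29 of 30 days at every visit hardly varies, yet the model assigns a variance of about 29.
- Real change between visits adds variance. With no random slope or visit-level effect, the model has nowhere to put it.

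Marijuana frequency, alcohol frequency and PSM misuse frequency are all outcomes named in the Study Methodology Overview. If the first feature dominates, standard errors are too wide and real effects are missed. If the second dominates, they are too narrow and chance differences are declared significant.

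**Working it through.** **1. Inputs.** From the documents: 600 per arm (Study 2) and 100 per arm (Study 3); coefficients -.13 and -.3; a 30-day window; ten items by inference. Two-sided 5% testing is assumed. Means, spread between students and change within students are not given, so all values below are assumptions, shown as ranges.

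**2. The plan's power figure.** With complete data, no site terms and one random intercept, the treatment-by-visit coefficient b is the log ratio of cell totals. Its model variance is the sum of 1/total over four cells, or (3 + 1/exp(b)) / (n × mean).

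- Study 2: (3 + 1/.878)/(600 × 3.2) = 4.139/1,920 = .00216, SE .0464. Then .13/.0464 = 2.80 and power = Phi(2.80 - 1.96) = .80.
- Study 3: (3 + 1/.741)/(100 × 3.79) = 4.350/379 = .0115, SE .107. Then .3/.107 = 2.80, power .80.

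The stated power thus needs a mean of about 3.2 (Study 2) or 3.8 (Study 3) if the variance is exactly Poisson. The plan does not give its intercept or random-effect variance, so the figure cannot be confirmed.

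**3. Direction of error, algebraically.** For a score out of K with probability p, constant within a student, the variance is Kp(1-p) and the Poisson SE is too large by 1/sqrt(1-p): 1.05 at 3 of 30 days and 1.41 at 15 of 30. If p varies between visits, the variance is Kp(1-p) + K(K-1)Var(p). This equals the Poisson value Kp when the within-student coefficient of variation of p is 1/sqrt(K-1): .19 for 30 days, .33 for ten items. Above that, the Poisson SE is too small.

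For one student at p = 29/30:

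- No breaks: the variance is 29 × 1/30 = .97 against 29, ratio sqrt(29/.97) = 5.5.
- With 5% of windows at zero: mean 27.55, variance .95 × .97 + .95 × .05 × 29² = 40.9, ratio sqrt(27.55/40.9) = .82.
- With 10% at zero: mean 26.1, variance .9 × .97 + .9 × .1 × 29² = 76.6, ratio .58.

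**4. Simulation.** 600 per arm, two visits, no treatment effect. Entries are model SE divided by true SD, with type I error in brackets where recorded.

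| Assumed outcome | Level fixed within student | Level changes between visits |
|---|---|---|
| PSM days, mean about 3.1 of 30 | 1.14 (2.9%) | log-SD .3: .86 (9%); .5: .65 (20%); .8: .49 (35%) |
| PSM days, misuse in only some windows | 1.09 (3.2%) | 80% of windows: .72 (16%); 60%: .51 (32%); 50%: .45 (38%) |
| Ten-item score, mean about 2.5 | 1.26 (1.5%) | log-SD .3: 1.04 (4%); .5: .85 (9%); .8: .71 (16%) |
| Marijuana days, 20% near-daily, mean about 8 | 1.93 | logit SD .5: 1.34; .8: 1.01; 1: .85 |
| Marijuana days, 20%, 35%, 50% near-daily | 1.84, 2.15, 2.55 | 5% zero windows: .89, .83, .90 (8%-10%); 10%: .61-.70 (17%-24%) |
| Alcohol days, mean 6-10 | 1.12-1.27 | logit SD .3: .94-1.07; .5: .80-.83 |

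A separate set of runs under other assumptions crossed 1 in the same way: 1.15 to .53 for PSM days, 1.22 to .53 for alcohol and 1.27 to .80 for the ten-item score. Marijuana gave 1.3 to 2.5 for steady users with 10%-35% near-daily, and .60 to .63 with 10% zero windows.

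**5. Consequences.** If the SE is too large by a factor r, an effect with 80% power under a correct SE is detected with probability Phi(2.80 - 1.96r): .64 at r = 1.25 and .52 at 1.4. If it is too small, type I error is 2 × (1 - Phi(1.96r)): 8% at r = .9 and 17% at .7.

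**6. Remedies tried.** Participant-clustered robust SEs brought type I error to about 4%-6% in every scenario. A beta-binomial mixed model gave SE/SD of about .9 to 1.2. Both were tried at 600 per arm, not at Study 3's 100 per arm.

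**The case against.** A reader might infer from the ceilings that Poisson standard errors are typically too large here and that the harm is lost power. The documents do not support that.

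- The reading requires students who hardly change between visits. Nothing describes such students. The section on alcohol and marijuana comorbidity calls PSM misuse episodic and ties it to exam periods, and eligibility needs only one misuse in the past month. At that level 0%-1% of simulated values reached 30, so the ceiling scarcely acts on PSM days.
- For marijuana, the statement "up to 90% of past-year PSM misusers reporting using other drugs, particularly marijuana" concerns any use of other drugs, not near-daily use. The near-daily shares above are assumptions, and follow-up to 18 months leaves room for breaks: zeros in 5% of windows were enough to reverse the direction.
- For alcohol days, modest visit-to-visit change also reverses it.

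A reader might also infer that the error damages the mediation analysis. It does not follow. There, alcohol and marijuana use enter the PSM model as visit-level covariates. Mediation is judged by how far the treatment effect shrinks, with a bootstrap described for the indirect path. The standard error of a separate marijuana outcome model plays no part.

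These objections remove the one-directional claim, not the underlying fault. The variance is still fixed at the mean, and no check or remedy is planned.

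**Conclusion.** The point holds as a two-directional one. Standard errors and p-values from the planned model will generally be wrong for the bounded outcomes. They are too large for steady, high-frequency outcomes such as near-daily marijuana use, or for a stable item score: about 1.3 to 2.5 times for the former and about 1.3 times for the latter. They are too small where use changes between visits, with ratios of about .5 to .9. That is the likelier case for PSM misuse and a possible one for alcohol.

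The sizes rest on assumed means, spreads and visit-to-visit variation; the document-based part is the model, the 30-day window and, by inference, the ten items. Open-ended quantities such as drinks have no comparable ceiling, but the same lack of free variance applies to them.

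**What to change.** Amend the Aim 2 text on use and consequence outcomes, and carry the change into Aim 3, by one of two routes.

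1. Model 30-day use days as days out of 30, and fixed-item totals such as the DAST as items endorsed out of the number of items, with a beta-binomial mixed model and the same visit, site and treatment-by-visit terms. Keep count models for open-ended counts. State the number of DAST items. A negative binomial or visit-level random effect is not a substitute for the bounded outcomes, because it can only add variance to the Poisson.
2. Keep the log-link model and its rate ratios, and base inference for all these outcomes on participant-clustered robust or participant-bootstrap standard errors, which correct errors in either direction.

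Route 1 costs a different model family and reporting as odds ratios plus a model-predicted difference in days or items. Route 2 costs slightly more analysis work. Where the Poisson errors were too small, correct ones will show lower power. In the simulated PSM case (mean about 3.1, coefficient -.13), power with a correct SE was .65 at within-student log-SD .3 and .44 at .5, against the planned .80. The power simulations should therefore be rerun with the chosen method.
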